6.9. Prior and Concomitant Medication

6.9.1. Allowed concomitant treatment

Allowed Concomitant Medications are:

- Corticosteroids at stable dose of prednisone or prednisone equivalent ≤ 20 mg/day; beclomethasone dipropionate (≤ 5 mg/day) or budesonide MMX (≤ 9 mg/day);
- Oral 5-aminosalicylic acid at stable dose;
- Immunosuppressants in the form of azathioprine, 6-mercaptopurine, or methotrexate at stable dose;
- Antidiarrheals (e.g., loperamide, diphenoxylate with atropine) at stable dose.

Potential other concomitant medications should be kept at constant dose during the course of the study and properly reported in the medical file of the patient and the eCRF.

This information should include the name of the medication (international nonproprietary name), daily dosage, duration, indication and the time of last intake before all PK samplings.

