7.2. Premature trial discontinuation

A patient can be withdrawn at any time from the study for the following reasons:

- Investigator's decision; patient that would experience a treatment failure during the study may be withdrawn at any time. S/he will have to be treated according to standard of care as soon as s/he is off from study treatment;
- An Adverse Event or an intercurrent condition that preclude continuation of treatment;
 - Specifically, an increase $\geq 3.0 \times$ ULN in liver transaminases (AST/SGOT and/or ALT/SGPT) or an increase $\geq 2.0 \times$ ULN in Alkaline phosphatase or in total bilirubin requires close observation with repeating liver enzymes and serum bilirubin tests two times weekly and clinical investigation to understand the etiology of this elevation. Frequency of retesting can decrease to once a month if the abnormality stabilizes after this initial two weeks of follow-up and if the patient is asymptomatic. Discontinuation of the study treatment should occur if:
 - ALT or AST $> 8 \times$ ULN
 - ALT or AST $> 5 \times$ ULN for more than 2 weeks
 - ALT or AST $> 3 \times$ ULN and total bilirubin $> 2 \times$ ULN or INR > 1.5
 - ALT or AST $> 3 \times$ ULN with appearance of fatigue, nausea, vomiting, right upper quadrant pain or tenderness, fever, rash, and/or eosinophilia ($> 5\%$).
- Worsening of the UC defined, from Week 8 onwards, as a 2-point increase in the pMMS, with pMMS ≥ 4 on 2 separate occasions 7 day-apart and confirmed by an endoscopy sub-score of 2 points or higher;
- Major protocol violation;
- Patient's decision;
- Withdrawal of consent;

A patient who prematurely exits the study will not be replaced.

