9.2. Efficacy Analysis

Analysis of efficacy data will be carried out in the Full Analysis Set in which subjects who prematurely discontinue the study due to adverse reaction(s) will be considered treatment failures.

The primary efficacy endpoint of the study is the change in the Modified Mayo Score (MMS) from Baseline to Week 8. This change will be compared between subjects who received ABX464 and placebo for each ABX464 treatment arm separately using an ANCOVA model adjusting for randomized study treatment arm, previous biological or JAK inhibitors treatment use (i.e. randomization strata), and baseline MMS.

The dose testing will commence with comparing the ABX464 50mg dose with placebo. If this is significant at a 5% two-sided level (i.e. $p < 0.05$) a comparison against placebo will be carried out at the ABX464 100mg dose. Again, if significance at a 5% level for this test is observed the procedure will be repeated at the ABX464 25mg dose. In this closed procedure no adjustment for multiple comparison is needed. Should the data warrant it, testing between doses may also be conducted.

In addition, descriptive statistics will be presented by treatment arm for all secondary efficacy variables for each measurement timepoint.

These statistics include:

- Continuous variables: mean, standard deviation, minimum and maximum, 95%
- Confidence intervals for the mean, median and quartiles will be presented.
- Categorical variables: counts, rates and 95% confidence intervals for the rates will be calculated.

In addition to descriptive statistics, the following analyses will also be carried out for the variables indicated below:

- The global (combined) ABX464 treatment effect vs. placebo in the change from Baseline in Modified Mayo Score at Week 8
- The proportion of subjects with clinical remission at Week 8 will be compared across study treatment arms using a stratified Mantel-Haenszel test.
- Mixed model analysis of covariance will be conducted for the following measurements:
 - The change from baseline in microRNA-124 levels in total blood (PAXgene®) at Week 1, Week 4, Week 8 and Week 16 and in tissue (RNA later).
 - The change from baseline in fecal calprotectin levels at Week 8 and Week 16.
 - The change from screening in the histopathology/infiltrate (rectal/sigmoidal biopsies) assessed by the Robarts Histopathology Index, the Geboes and Nancy Histology Scoring Scales at Week 8 and Week 16 (if available).

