2.3. ESTIMANDS

The primary and secondary estimands to support regulatory decisions are described in Table A below. The intercurrent event is the early discontinuation of patients from the study and/or missing Week 8 efficacy assessments.

Table A List of Estimands

Document: \\ieddc-vnasc01\BIOSdata\Abivax\ABX464\FZA92720\Biostatistics\Documentation\SAP\ABX464-103_SAP_V2.0_10MAY2021

Author: [REDACTED]

Version Number: 2.0
Version Date: 10May2021

Template No.: CS_TP_BS016 Revision 5

Reference: CS_WI_BS005

Effective Date: 01Apr2018

Estimand	Definition	Attributes			
		Population	Variable/Endpoint	Intercurrent event handling strategy	Population-level summary measure
Primary	Optimal ABX464 dose	All patients randomized, received at least one dose of study drug and provided at least one efficacy data point	Mean change in MMS from baseline to Week 8	Missing Week 8 MMS components (stool frequency, rectal bleeding and endoscopy subscores) will be imputed using methods detailed in section 7.3.	Mean change from baseline
Secondary	The effect of different dose groups vs placebo on secondary variables	All patients randomized, received at least one dose of study drug and provided at least one efficacy data point	Mean change from baseline to Weeks 8 and 16 in pMMS	Missing Week 8 pMMS components (stool frequency and rectal bleeding subscores) will be imputed using methods detailed in section 7.3.	Mean change from baseline
			Clinical remission or response at Weeks 8 and 16	Patients with missing Week 8 assessment will be considered non-responders	Proportion of responders in each treatment group
			Mean change from baseline to Week 8 in fecal calprotectin and CRP levels	Missing fecal calprotectin and CRP values will not be imputed.	Mean change from baseline

Document: \\ieddc-vnasc01\BIOSdata\Abivax\ABX464\FZA92720\Biostatistics\Documentation\SAP\ABX464-103_SAP_V2.0_10MAY2021

Author: [REDACTED]

Version Number: 2.0
 Version Date: 10May2021

Template No.: CS_TP_BS016 Revision 5

Reference: CS_WI_BS005

Effective Date: 01Apr2018

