7.3. MISSING DATA

A subject's missing efficacy data viz. MMS (or any components of MMS missing) at Week 8, will be imputed and the subject will be considered as a non-responder for clinical remission and response.

Missing MMS components at Week 8 will be imputed as follows:

Stool Frequency Sub score: The average of the 3 recent eDiary stool frequency records (if no prior records then choose records after the Week 8 visit date) within 10 days of date of week 8 visit is calculated. The normal stool frequency (at screening) is subtracted from the average and rounded to a whole number. The imputed sub score will be assigned as follows:.

Sub score=0; if calculated value =0

Sub score=1; if calculated value=1,2

Sub score=2; if calculated value=3,4

Sub score=3; if calculated value=5 or greater

If no records available within 10 days from eDairy, the nearest neighbour method will be considered.

Rectal Bleeding Sub score: The worst of the 3 recent eDiary records within 10 days of Date of Week 8 visit, will be considered as the analysis value (if no prior records then choose records after the Week 8 visit date) . If no records available within 10 days from eDairy, the nearest neighbour method will be

Document: \\iedc-vnasc01\BIOSdata\Abivax\ABX464\FZA92720\Biostatistics\Documentation\SAP\ABX464-103_SAP_V2.0_10MAY2021

Author: [REDACTED]

Version Number:
Version Date:

2.0
10May2021

Template No.: CS_TP_BS016 Revision 5

Reference: CS_WI_BS005

Effective Date: 01Apr2018

considered.

Mucosal appearance at Endoscopy: The analysis value of the nearest neighbour is used to impute missing Endoscopy sub score. The nearest neighbour is defined as the subject in Placebo arm with non-missing sub score, matching the 'subject with missing value' by Gender, Baseline MMS, Age and Previous Exposure to other biologics/JAK status. The matching score is calculated for all the placebo subjects with non-missing sub score, as follows:

- 1) If the subject matches in gender, 5 points assigned.
- 2) If previous exposure status matches, then additional 5 points.
- 3) The absolute difference between the Baseline MMS and Age, is subtracted from the scores.

The Placebo subject with the highest score is considered the nearest neighbour. In case of tied nearest neighbour scores, the worst sub score value will be used to impute.

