15.2.1. SECONDARY EFFICACY VARIABLES & DERIVATIONS

15.2.1.1. Number and Percentage of Patients in Clinical Remission at Week 8 and Week 16

Clinical remission is defined as:

- A stool frequency subscore = 0 or 1
- A rectal bleeding sub-score = 0
- An endoscopy sub-score = 0 or 1 (modified to exclude friability)

This endpoint will be calculated per treatment arm and presented descriptively.

Percentage of patients in clinical remission at Week 8

$$= \frac{\text{Number of patients in treatment arm with clinical remission at Week 8}}{\text{Total number of patients in the treatment arm}} \times 100$$

Percentage of patients in clinical remission at Week 16

$$= \frac{\text{Number of patients in treatment arm with clinical remission at Week 16}}{\text{Total number of patients in the treatment arm at Week 16}} \times 100$$

Percentage of patients in clinical remission at Week 8 or Week 16

$$= \frac{\text{Number of patients in treatment arm with clinical remission at Week 8 or Week 16}}{\text{Total number of patients in the treatment arm at Week 8 or Week 16}} \times 100$$

Number of patients with clinical remission at week8 and not at week 16 as well as number of patients with clinical Remission at Week 16 and not at Week 8 will also be presented.

Document: \\ieddc-vnasc01\BIOSdata\Abivax\ABX464\FZA92720\Biostatistics\Documentation\SAP\ABX464-103_SAP_V2.0_10MAY2021

Author: [REDACTED]

Version Number: 2.0
Version Date: 10May2021

Template No.: CS_TP_BS016 Revision 5

Reference: CS_WI_BS005

Effective Date: 01Apr2018

15.2.1.2. Combined Number and Percentage of Patients in Clinical Remission at Week 8 and Week 16

Clinical remission is defined in Section 15.2.1.1. The number and percentage of patients in clinical remission at both Week 8 and Week 16 will be summarized by treatment arm.

Percentage of patients in clinical remission at Week 8 and Week 16

$$= \frac{\text{Number of patients in treatment arm with clinical remission at Week 8 and Week 16}}{\text{Total number of patients in the treatment arm at both visits}} \times 100$$

15.2.1.3. Number and Percentage of Patients with Clinical Response at Week 8 and Week 16

Clinical response is defined as

- A reduction from baseline in MMS ≥ 2 points, and
- A reduction in MMS $\geq 30\%$ from baseline with a decrease in rectal bleeding sub-score ≥ 1 point or absolute rectal bleeding sub-score ≤ 1 point

This endpoint will be summarized by treatment arm.

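### A Full Analysis Set patient who adds or increases UC medication and still attends Week 8 can count as a remitter or responder, because no readable rule makes that a failure

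*SAP*

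**What the plan says.** **Events recognised.** SAP 2.3 states: "The intercurrent event is the early discontinuation of patients from the study and/or missing Week 8 efficacy assessments". For remission and response, Table A gives one handling rule: "Patients with missing Week 8 assessment will be considered non-responders". SAP 7.3 says that when the Week 8 MMS or any component is missing, "the subject will be considered as a non-responder for clinical remission and response"; SAP 15.1.2 repeats this. Protocol 9.2 adds one further failure rule, for the "Full Analysis Set in which subjects who prematurely discontinue the study due to adverse reaction(s) will be considered treatment failures".

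**Endpoint definitions.** SAP 15.2.1.1 defines remission by three sub-scores, the last being "An endoscopy sub-score = 0 or 1 (modified to exclude friability"). SAP 15.2.1.3 defines response by the fall in MMS and a rectal bleeding condition. Neither has a medication condition. FAS membership (SAP 5.2.3) needs only a dose of study drug and baseline data on one efficacy variable.

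**Medication rules.** Protocol 6.9.1 allows corticosteroids, oral 5-ASA and antidiarrheals at stable dose, and likewise "Immunosuppressants in the form of azathioprine, 6-mercaptopurine, or methotrexate at stable dose". Protocol 6.9.2 prohibits biologics, JAK inhibitors, topical corticosteroids, topical 5-ASA, cyclosporine and tacrolimus. Under Protocol 7.2 withdrawal for failure is optional: "patient that would experience a treatment failure during the study may be withdrawn at any time".

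**Per-protocol set.** SAP 5.2.4 lists prohibited medication up to Week 8 as a reason for exclusion. Criteria 12 (prohibited drugs) and 13 (unstable doses) are both decided case by case. SAP 15.2 repeats the secondary analyses in this set.

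**The concern.** Stable background therapy is a rule for running the trial, with no consequence for the FAS outcome. Someone who raises a steroid dose in Week 5, attends Week 8 and meets the score criteria is a remitter. Someone on unchanged therapy who lacks one Week 8 component is a failure. The SAP does not explain the difference.

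At stake is what the remission and response rates mean, and with them the Week 8 remission odds ratio for each dose against placebo (SAP 15.2.3.2). These can credit the assigned arm with successes reached on therapy that the protocol does not allow. The Week 16 rates have the same gap: Table A's rule for Weeks 8 and 16 mentions only a missing Week 8 assessment, and the prohibited-medication reason for per-protocol exclusion stops at Week 8.

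**Working it through.** **Step 1. Follow each type of patient through the written rules.**

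| Patient | Rule that applies | FAS Week 8 remission/response |
|---|---|---|
| Leaves before Week 8 for rescue, no endoscopy | SAP 2.3, 7.3: component missing | Non-responder |
| Leaves because of an adverse reaction | Protocol 9.2 | Failure |
| Attends Week 8, one MMS component missing | SAP 7.3 | Non-responder |
| Adds or increases UC therapy, stays, attends Week 8 | None readable; SAP 15.2.1 scores apply | Success if the scores qualify |

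The first row covers the expected rescue route. Protocol 7.2 links standard-of-care treatment to coming off study drug, and the End of Study procedures in Protocol 5.2.5 include the partial score but no sigmoidoscopy. The concern is confined to the last row.

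**Step 2. Does the per-protocol set close the gap?** In part. Membership is agreed before unblinding (SAP 5). Criterion 13's heading and stability rule refer to the period before screening or baseline, but its note brings in unstable-dose deviations found during the study. Exclusion is therefore possible but not assured, and it removes the patient from numerator and denominator alike. It never counts a failure. The concomitant-medication subgroup (SAP 7.5, 15.1.4.2) repeats the MMS analysis and reclassifies nobody.

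**Step 3. Size.** The plan gives no figure on this point, so there is none to reproduce. The only planned input is 61 per arm (Protocol 9.4; 244/4 = 61).

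- One affected remitter: 1/61 = 1.6 percentage points on that arm's Week 8 rate.
- Shift in the active-minus-placebo difference from counting such remitters: (affected active remitters − affected placebo remitters)/61.

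For illustration, assume the phase IIa remission rates (Protocol 1.3: 35.0% and 11.1%). Then 0.35 × 61 = 21.35, taken as 21, and 0.111 × 61 = 6.77, taken as 7. The unstratified odds ratio is [a × (61 − p)] / [(61 − a) × p], with a active and p placebo remitters. The number of affected remitters in each row is also assumed.

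| Remitters reclassified as failures | a vs p | Difference (points) | Odds ratio |
|---|---|---|---|
| None | 21 vs 7 | 14/61 = 23.0 | (21×54)/(40×7) = 4.05 |
| 1 placebo | 21 vs 6 | 15/61 = 24.6 | (21×55)/(40×6) = 4.81 |
| 2 placebo | 21 vs 5 | 16/61 = 26.2 | (21×56)/(40×5) = 5.88 |
| 1 active | 20 vs 7 | 13/61 = 21.3 | (20×54)/(41×7) = 3.76 |
| 2 active | 19 vs 7 | 12/61 = 19.7 | (19×54)/(42×7) = 3.49 |
| 1 in each arm | 20 vs 6 | 14/61 = 23.0 | (20×55)/(41×6) = 4.47 |

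One or two patients move the odds ratio visibly, in either direction. Equal numbers leave the difference unchanged but still alter the odds ratio.

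**The case against.** **Few patients may be affected.** A patient in the gap must break the medication rules, avoid withdrawal, attend Week 8 and meet the score criteria. This stands. Nothing in the documents suggests that there will be many.

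**The endpoints are secondary.** The gatekept testing (SAP 7.4) concerns MMS only, and this is a phase IIb study. This also stands, and it limits the importance of the point.

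**Using observed scores is a legitimate strategy.** A treatment-policy approach is coherent, and calling the same patient improved on MMS but a failure on remission may look inconsistent. This stands only in part. The SAP neither states nor defends that strategy for added therapy. It also already separates the two kinds of endpoint: a missing Week 8 component is imputed for MMS, but makes the patient a non-responder for remission and response. A failure rule for added therapy follows the same pattern.

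**The per-protocol set is working as intended.** Excluding deviators is its purpose, and Criterion 13's note already reaches on-study dose changes. This stands, so rewording that criterion is not needed.

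**The illustration is fragile.** The phase IIa placebo group had 9 patients, so 11.1% is one remitter. This stands. The table shows sensitivity and is not a forecast.

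**Redaction.** Parts of SAP 5.1 and 15.2.3.1 are blacked out and could contain relevant handling. This cannot be resolved from the public text.

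**Conclusion.** On the readable text the gap is real but narrow. It concerns FAS patients who add or increase UC therapy, or take a prohibited UC drug, remain in the study and attend Week 8, with the same gap up to Week 16 for the Week 16 rates. The written rules allow them to count as remitters or responders. It should be fixed because the fix is cheap, not because harm has been shown. Confidence is medium because of the redactions.

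A reader might infer three stronger things that the documents do not support:

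- **The plan inflates the benefit of ABX464.** No rate of medication change is given for any arm. Counting these successes favours whichever arm has more of them, and that could be placebo.
- **Rescued patients in general are counted as successes.** Those who leave before Week 8 without an endoscopy are already non-responders.
- **The primary result is compromised.** The MMS analysis also uses observed Week 8 scores regardless of medication, but that is a coherent choice and can stay as planned.

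The size is 1.6 points per affected remitter, assuming 61 FAS patients in the arm. The number affected is unknown.

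**What to change.** 1. In SAP 2.3 and 7.3, name the following as an intercurrent event for remission and response: starting or increasing a corticosteroid, 5-ASA or immunosuppressant for UC after first dose, or taking a UC drug prohibited by Protocol 6.9.2. Count the patient as a non-remitter and non-responder at Week 8 if it occurs by Week 8, and in the Week 16 rates if it occurs by Week 16.
2. Treat newly started or increased antidiarrheals the same way, or state why not. They are also allowed only at stable dose and act directly on stool frequency.
3. Identify cases at the blind data review, before unblinding. Use the SAP Appendix 5 classes, and list TNF inhibitors, vedolizumab, other biologics and JAK inhibitors by name from Protocol 6.9.2, since Appendix 5 covers only 5-ASA, corticosteroids and immunosuppressants.
4. First confirm that dose and indication are in the database. Protocol 6.9.1 requires "daily dosage, duration, indication and the time of last intake before all PK samplings" to be recorded, but the medication fields named in SAP Criteria 12 and 13 include neither dose nor indication.
5. Keep the observed-score rates as a sensitivity analysis.

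The cost is SAP wording, a derived flag and a short blinded medication review. The downside is slightly lower remission and response rates. Patient care and the primary analysis do not change.

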3. STUDY DESIGN

3.1. GENERAL DESCRIPTION

This is a randomized, double blind, placebo controlled, parallel group, multiple dose, induction study to evaluate the safety, tolerability of ABX464 compared with placebo in patients with moderate to severe ulcerative colitis who have inadequate response, loss of response, or intolerance with at least one of the following agents: immunosuppressant treatment (i.e. azathioprine, 6-mercaptopurine, methotrexate), TNF- α inhibitors, vedolizumab, JAK inhibitors and/or corticosteroid treatment. This phase IIb study will evaluate the efficacy and the safety of three dose-levels of ABX464, administered daily, in improving MMS in patients at Week 8.

Approximately 244 patients from 110 to 150 sites in Europe, Canada and United States of America (US) will participate in this study. Eligible patients from non-US sites will be randomized 1:1:1:1 into four parallel intervention/treatment groups as described in Table B. Patients in the US will be randomized 1:1:1 to 25 mg, 50 mg and placebo treatment groups. Approximately 61 patients will be randomized to each study treatment arm.

Table B Treatment Groups

Intervention/treatment Active Arm	
Group #1: 25mg once daily (q.d)	1 capsule of 25mg ABX464 + 1 capsule of Placebo
Group #2: 50mg q.d	1 capsule of 50mg ABX464 + 1 capsule of Placebo
Group #3: 100mg q.d	2 capsules of 50mg ABX464
Group #4: Placebo q.d	2 capsules of Placebo

Randomization will be stratified by:

- US vs non-US patients
- Previous exposure and non-exposure to biological drugs or JAK inhibitors.

Document: \\iedc-vnasc01\BIOSdata\Abivax\ABX464\FZA92720\Biostatistics\Documentation\SAP\ABX464-103_SAP_V2.0_10MAY2021

Author: [REDACTED]

Version Number: 2.0
Version Date: 10May2021

Template No.: CS_TP_BS016 Revision 5

Reference: CS_WI_BS005

[figure not shown]
Effective Date: 01Apr2018

The proportion of patients with previous exposure to biologics or JAK inhibitors will be limited to 60%; including a maximal proportion of patients with previous treatment with vedolizumab of 20%. The maximal proportion of patients with previous exposure to JAK inhibitors will be limited to 10%.

Patients will be treated for 16 weeks in this induction study. All endoscopies (videos) will be centrally reviewed. E-Diaries will be used to collect frequency of stools, rectal bleedings, number of capsules taken and the intake time.

Flexible sigmoidoscopy with rectal and/or sigmoidal biopsies will be performed at screening, at Day 57 +/- 4 days (Week 8) and at Day 113 +/- 4 days (Week 16). The Day 113 measurement will only be taken if the patient does not experience endoscopic improvement (i.e. endoscopy sub-score of 2 or 3) at Day 57. In the event of clinical progression of the disease after Week 8, defined as at least a 2-point increase from screening in pMMS, with a MMS ≥ 4 confirmed by an endoscopy sub score of 2 points or higher, the patient will exit the study.

Study Design

Document: \\ieedc-vnasc01\BIOSdata\Abivax\ABX464\FZA92720\Biostatistics\Documentation\SAP\ABX464-103_SAP_V2.0_10MAY2021

Author: [REDACTED]

Version Number: 2.0
Version Date: 10May2021

Template No.: CS_TP_BS016 Revision 5

Reference: CS_WI_BS005

Effective Date: 01Apr2018

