6.4. Method of Assigning Patients to Treatment Arms

All patients will be assigned a unique and incremental Patient Identification (ID) number. Patient IDs will be unique (i.e. reallocation of the ID will not be permitted). The format will be a seven-digit number as follows: ABX-country/site number (4 digits) – Patient number (3 digits). The latter 3-digit Patient number will be assigned according to the patient's order of inclusion in the center.

Eligible non-US patients (i.e. those who fulfil all inclusion/exclusion criteria) will be randomized according to a 1:1:1:1 ratio to ABX464 100mg: ABX464 50mg: ABX464 25mg: placebo treatment arms.

Randomization will be performed via IWRS. Treatment numbers will be allocated first at randomization and then every month (i.e. D29, D57 and D85).

In all cases, patient should return his/her used and unused blister cards at each study visit for a compliance check.

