9.4. Determination of Sample Size

The primary endpoint is the change in the Modified Mayo Score (MMS) from Baseline to Week 8. The primary endpoint will be compared between subjects who received ABX464 and placebo for each ABX464 treatment arm separately.

For the sample size calculation, the following assumptions were made:

- mean reduction in MMS (ABX464): 2.5
- mean reduction in MMS (placebo): 1.0
- pooled standard deviation of reduction in MMS: 2.1
- Type 1 error: 5% two-sided.
- Treatment testing to use a sequential, gate-keeping strategy, where treatment arms will be tested in the following order: ABX464 50mg vs. placebo, ABX464 100mg vs. placebo, ABX464 25mg vs. placebo. Subsequent tests will only be performed only if prior test(s) are significant ($p<0.05$).
- >90% power
- Two-sample t-test
- 5% dropout rate prior to Week 8 MMS assessment (all treatment arms)
- 1:1:1:1 (ABX464 100mg: ABX464 50mg: ABX464 25mg: placebo) study treatment arm allocation ratio.

If the above assumptions hold true, then a total sample size of 232 subjects will be required to be randomized (58 subjects randomized to each study treatment arm).

Due to the SARS Cov-2 pandemic the drop-out rate of the study is expected to be somewhat higher than originally estimated. Therefore, an additional 12 subjects are planned to be recruited in the study leading to an overall sample size of 244 patients (61 subjects randomized to each study treatment arm).

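### Arms of about 61 and a 1:1:1:1 ratio cannot hold once US patients are randomised without 100 mg, and the primary model leaves out the region factor that this makes necessary

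*SAP*

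**What the plan says.** **Allocation.** SAP 3.1 gives 1:1:1:1 for non-US sites. It then says "Patients in the US will be randomized 1:1:1 to 25 mg, 50 mg and placebo treatment groups", and next "Approximately 61 patients will be randomized to each study treatment arm", out of roughly 244. SAP 15.2.3.3 confirms that US patients do not receive 100 mg. Protocol 6.4 gives its 1:1:1:1 ratio for "Eligible non-US patients" and states no ratio for US patients.

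**Sample size.** Protocol 9.4 lists "1:1:1:1 (ABX464 100mg: ABX464 50mg: ABX464 25mg: placebo) study treatment arm allocation ratio" with no US exception and arrives at 61 per arm. The synopsis does the same. The only power figure in either place is above 90%.

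**Model.** US versus non-US is a randomisation stratum (synopsis, Protocol 3.1.1, SAP 3.1 and 7.2). The synopsis includes it in the primary ANCOVA. Protocol 9.2 and SAP 15.1.3 do not, and SAP 7.1 does not list it among the factors. SAP 3.3 does not mention the difference from the synopsis. SAP 15.2.3.3 omits it from the MMRM and gives as the reason that US patients do not get 100 mg.

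No document states the expected number of US patients, the expected size of the 100 mg arm, or a power specific to 100 mg.

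**The concern.** The three allocation statements in SAP 3.1 cannot all be true unless no US patient is enrolled, and the US is a planned region with its own stratum. The 100 mg comparison is the second step of the ordered tests, and 25 mg is tested only if it succeeds. A reader who relies on 61 per arm will misjudge how much information there is on 100 mg.

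The second issue follows from the first. Some placebo patients come from the US, and no 100 mg patient does. A model without region compares a non-US arm with a mixed-region arm. Any US/non-US difference in MMS change that baseline MMS and prior biologic or JAK exposure do not explain then enters the 100 mg estimate. The 25 mg and 50 mg contrasts are protected, because the US allocation is equal across those arms and placebo. The primary objective is to choose a dose, so a distortion confined to one dose matters.

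**Working it through.** **Inputs (Protocol 9.4).** "mean reduction in MMS (ABX464): 2.5"; "mean reduction in MMS (placebo): 1.0"; so the difference is 1.5. "pooled standard deviation of reduction in MMS: 2.1". "Type 1 error: 5% two-sided". Two-sample t-test; 5% dropout before Week 8, later expected to be somewhat higher with no figure given. As a second dropout case I take 9.8%, which leaves 55 of 61 evaluable.

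**Reproducing the plan.** 58 per arm less 5% is 55 evaluable, and noncentral-t power is 96.0% per comparison. 61 per arm less 5% is about 58, and power is 96.8%. The stated figure of more than 90% is met with equal arms.

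**Arm sizes.** With U US patients in 244:

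- 100 mg arm: (244 − U)/4
- each other arm: (244 − U)/4 + U/3
- US fraction of placebo: p = (U/3) ÷ [(244 − U)/4 + U/3]

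Example at 20%: U = 48.8; 100 mg = 195.2/4 = 48.8; others = 48.8 + 16.3 = 65.1; p = 16.3/65.1 = 25%.

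**Power for 100 mg against all placebo, no region factor:**

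| Assumed US share | 100 mg arm | Each other arm | US share of placebo | Power, 5% dropout | Power, 9.8% dropout |
|---|---|---|---|---|---|
| 0% | 61 | 61 | 0% | 96.8% | 96.0% |
| 5% | 58 | 62 | 7% | 96.5% | 95.7% |
| 10% | 55 | 63 | 13% | 96.2% | 95.4% |
| 20% | 49 | 65 | 25% | 95.4% | 94.4% |
| 30% | 43 | 67 | 36% | 94.1% | 92.9% |
| 40% | 37 | 69 | 47% | 92.1% | 90.7% |

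Power first falls below 90% at U = 116 (48%) with 5% dropout, or U = 104 (43%) with 9.8%. The simulated probability that all three ordered tests succeed, at 5% dropout, is 92.4% with no US patients and 92.3% at 20% US.

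**Effect of omitting region.** If US and non-US patients differ by D points in MMS change after the other covariates, the 100 mg contrast shifts by about p × D. For an illustrative D of 1 point at 20% US, the shift is 0.25 × 1 = 0.25 points, or 0.25/1.5 = 17% of the planned difference. Its direction is unknown.

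**Cost of including region.** In an additive model with common SD σ, the variance of the 100 mg contrast is

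σ²[1/n₁₀₀ + 1/n_placebo + p²(1/U + 1/(3n₁₀₀))].

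At 20% US the bracket is 0.02049 + 0.01537 + 0.0625 × (0.02049 + 0.00683) = 0.03757, against 0.03586 without region: 4.8% more variance. At 10, 20 and 30% US, power with the factor is 95.9, 94.5 and 92.5% at 5% dropout, and about 95, 93 and 91% at 9.8%. It falls below 90% from U = 94 (39%) or U = 83 (34%). This takes region as explaining no variance; if it does explain some, the cost is smaller.

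**The case against.** The strongest reply is that nothing the plan promises about power is broken. A reader might infer from a smaller 100 mg arm that its power is overstated, or that the ordered tests are undermined. The documents do not support either reading. The only stated power is above 90%, the placebo arm grows as the 100 mg arm shrinks, and the probability of passing all three tests hardly changes.

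A reader might also infer that 100 mg has to be tested only against non-US placebo, and cite power of 0.87. That figure needs a 30% US share, roughly 10% dropout and a restricted control group, and none of these is in the plan. The restriction itself causes the loss: at 30% US and 5% dropout it takes power from 94.1% to 88.8%. A region factor gives protection at less cost.

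Three further points stand. SAP 3.1 does not claim 1:1:1:1 for everyone; it limits that ratio to non-US sites, and the unqualified version is in Protocol 9.4 and the synopsis. The per-arm figure is approximate, and at 5% US the arms of 58 and 62 fit it fairly. SAP 3.3 drops the country and US/non-US subgroups because some countries contribute few patients. It does not name the US, so it shows neither a small nor a large US share.

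The reply does not cover the model. SAP 15.2.3.3 treats the missing 100 mg arm as grounds for leaving region out. That missing arm is what links region to treatment, so it is grounds for including region.

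**Conclusion.** The point holds for arm size, allocation and the model, and not for the stated power. Within a total of 244, arms of 61 and an unqualified 1:1:1:1 require that no US patient be randomised. At an assumed 10–30% US, the 100 mg arm is 55 down to 43 and each other arm 63 up to 67. That range is my assumption, since no document gives a US number; with a very small US share the discrepancy is only one of wording.

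The omission of US/non-US from the primary ANCOVA conflicts with the synopsis and leaves the 100 mg contrast open to a region difference, weighted by the US fraction of placebo (about 13–36% over the same range). Whether such a difference exists cannot be known from the documents. This should be corrected, but it does not invalidate the design.

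**What to change.** 1. In Protocol 9.4, the synopsis and SAP 3.1, state the expected number of US patients, the resulting size of each arm, and the power for 100 mg under the model to be used. Replace the flat figure of 61 per arm.
2. State the US allocation in Protocol 6.4 so that it agrees with SAP 3.1, and mark 1:1:1:1 as applying to non-US patients in Protocol 9.4 and the synopsis. Keep the non-US sentence in SAP 3.1, which is correct.
3. Include US/non-US as a factor in the primary ANCOVA (Protocol 9.2, SAP 7.1 and 15.1.3), as the synopsis already does, and in the MMRM. Delete the reason given in SAP 15.2.3.3 for omitting it.
4. Keep all placebo patients as the control in the primary 100 mg comparison. Non-US placebo alone may be reported as a sensitivity analysis at most.

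Cost: text changes, one model degree of freedom, and a small loss of precision for 100 mg (about 2, 5 and 7% more variance at 10, 20 and 30% US). No extra patients are needed. If 61 patients in the 100 mg arm is itself a requirement, 244 non-US patients are needed and the total becomes 244 + U.
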